6.3.7.2. Analysis

By visit analysis of change from baseline will be conducted based on the treatment policy estimand, in addition to the by visit analyses based on the primary efficacy estimand. A mixed model repeated measures (MMRM) analysis will be performed using the change in SQLS score from baseline as the dependent variable, and treatment arm, study visit, treatment-by-visit interaction, stratification variables (sex and geographic region), age, and SQLS total score at baseline as covariates. An unstructured covariance matrix will be used in all models. Analyses will be performed in SAS using the Kenward-Roger option to estimate the denominator degrees of freedom and standard errors.

[figure not shown]
Only SQLS scores recorded while the subject was receiving randomized treatment will be included in the analysis. Any values recorded after withdrawal from randomized treatment will be set to missing. No multiple imputation will be used.

6.3.8. PSP Score – Change From Baseline to Weeks 4

A mixed model repeated measures (MMRM) analysis for Period 1 will be performed using the change in PSP score from baseline as the dependent variable, and treatment arm, study visit, treatment-by-visit interaction, stratification variables (sex and geographic region), age, and PSP score (if applicable, if the model does not converge this covariate will not be used) at baseline as covariates. An unstructured covariance matrix will be used in all models. Analyses will be performed in SAS using the Kenward-Roger option to estimate the denominator degrees of freedom and standard errors. Least squares mean and 95% CI of change in PSP Score from baseline to Week 4 and Week 8 will be generated.

Only PSP scores recorded while the subject was receiving randomized treatment will be included in the analysis. Any values recorded after withdrawal from randomized treatment will be set to missing. No multiple imputation will be used.

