1.2.3. Estimand Using the Treatment Policy Strategy

As supplementary analyses (Section 10.5.6.3 in the Protocol), the primary and key secondary objectives will be evaluated where all ICEs are handled using the Treatment Policy strategy (i.e., all available data will be analyzed regardless of ICE). *The estimand attributes for treatment, population, endpoint and population-level summary will be the same as described in the Primary Estimand and Key Secondary Efficacy Estimand sections*, respectively. This estimand addresses the following clinical question of interest: "What is the treatment benefit of a patient regardless of treatment adherence or early discontinuation over 8 weeks?".

In addition to the primary and key secondary endpoints, the other secondary efficacy endpoints in Period 1 will also be analyzed according to this estimand: PANSS, CGI-I, CGI-S, PGI-I, SQLS, PSP, and [REDACTED] (Section 6.4 and Appendix D).

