1.2.4. Estimand using a Modified Treatment Policy Strategy

As additional supplementary analyses, the primary and key secondary objectives will be evaluated using the Treatment Policy strategy except that efficacy data after the ICE for use of antipsychotic medication during Period 1 will not be used (i.e., they will be defined as missing in the analysis dataset). *The estimand attributes for treatment, population, endpoint and population-level summary will be the same as described in the Primary Estimand and Key Secondary*

Efficacy Estimand sections, respectively. The clinical question of interest is as follows: “What is the treatment benefit of a patient diagnosed with schizophrenia who did not receive any other antipsychotic medication regardless of early discontinuation for 8 weeks?”. The rationale for this estimand is to evaluate the treatment effect of TV-44749 versus placebo on efficacy endpoints, which is not confounded by concomitant use of other antipsychotics from baseline to week 8.

In addition to the primary and key secondary endpoints, the other secondary efficacy endpoints in Period 1 will also be analyzed according to this estimand: PANSS, CGI-I, CGI-S, PGI-I, SQLS, PSP, and [REDACTED] (Section 6.4 and Appendix D).

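### SAP 6.3.7.2 and 6.3.8 drop SQLS and PSP scores recorded after treatment withdrawal, although SAP 1.2.3, 1.2.4 and 6.3 promise treatment-policy and modified treatment-policy analyses that keep them

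*SAP*

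**What the plan says.** **SQLS (SAP 6.3.7.2).** The by-visit analysis of change "will be conducted based on the treatment policy estimand, in addition to the by visit analyses based on the primary efficacy estimand". After the model description the section adds "Only SQLS scores recorded while the subject was receiving randomized treatment will be included in the analysis", followed by "Any values recorded after withdrawal from randomized treatment will be set to missing. No multiple imputation will be used".

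**PSP (SAP 6.3.8).** No estimand is named. The section says "Least squares mean and 95% CI of change in PSP Score from baseline to Week 4 and Week 8 will be generated", then "Only PSP scores recorded while the subject was receiving randomized treatment will be included in the analysis", and repeats the two sentences on setting later values to missing and not imputing.

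**Estimands (SAP 1.2.3, 1.2.4).** Under treatment policy "all available data will be analyzed regardless of ICE", and the other secondary endpoints in Period 1 "will also be analyzed according to this estimand: PANSS, CGI-I, CGI-S, PGI-I, SQLS, PSP". Modified treatment policy removes efficacy data after other antipsychotic use and asks about the benefit for a patient "who did not receive any other antipsychotic medication regardless of early discontinuation for 8 weeks". It covers the same endpoints.

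**Allocation of estimands (SAP 6.3, 17.3, Appendix D).** Section 6.3 requires by-visit PSP under its own estimand and both policy estimands. The remaining secondary endpoints, which include SQLS, get the two policy estimands only. The visible Appendix D row for week-8 PSP ticks both policy columns. Section 17.3 says treatment policy has taken the place of the while-on-treatment estimand.

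**The concern.** A rule that admits only on-treatment scores is a while-on-treatment rule. It cannot be applied together with a treatment-policy estimand, which keeps scores after discontinuation. For SQLS the two instructions stand in the same section.

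If the rule is followed, the SQLS and 6.3.8 PSP results answer what happens while patients remain on treatment. The stated question in 1.2.3 concerns benefit whether or not patients adhere or stop early. Two analysts working from this SAP could each cite a section and produce different results.

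Two related conflicts arise:

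- 6.3.7.2 adds a primary-estimand SQLS analysis. Section 6.3 excludes it, and the primary estimand as specified in 6.2.3 uses the multiple imputation that 6.3.7.2 bars.
- 6.3.8 produces a non-imputed week-8 PSP estimate without naming its estimand. It can differ from the key secondary week-8 PSP result obtained under 6.3.2.2.

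**Working it through.** The SAP gives no figure to reproduce here, so the main check compares texts. The arithmetic only gives scale.

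**1. What each rule does with a score**

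| Score | Treatment policy (1.2.3) | Modified treatment policy (1.2.4) | 6.3.7.2 and 6.3.8 |
|---|---|---|---|
| After withdrawal, no other antipsychotic | keep | keep | set to missing |
| On treatment, after other antipsychotic use | keep | drop | keep (no rule to drop) |

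The written rule departs from treatment policy in the first row and from modified treatment policy in both.

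**2. Is there another estimand the rule could serve?**

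- The while-on-treatment efficacy estimand was replaced (17.3).
- The While on Treatment period in 8.1 is confined to listed safety variables and does not cover SQLS or PSP.
- The primary estimand removes scores after treatment discontinuation. It also removes scores after non-short-term prohibited antipsychotic use and then imputes, and the rule does neither.

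No efficacy estimand in SAP 1.2 matches the rule.

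**3. Do scores exist for the rule to remove?**

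- Patients who stop are encouraged to attend the ET, EOT and FU visits (Protocol 5.4; SAP 2.1).
- PSP and SQLS are scheduled at ET and EOT (Protocol Table 1 and Appendix B).
- SAP 4.4 maps an ET or EOT result to a missing scheduled visit when it falls in that visit's window.
- EOT is 4 weeks after the last dose, ±1 week (Protocol Table 1, footnote b). Dosing visits have a ±3-day window, with up to 5 days early in exceptional cases (footnote f).

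| | After one injection (Day 1) | After two (Day 29) |
|---|---|---|
| Nominal EOT | 1 + 28 = Day 29 | 29 + 28 = Day 57 |
| Allowed EOT days | 22–36 (15 days) | 50–64 (15 days) |
| Target visit window, ±3 days | Visit 7: 26–32 (7 days) | Visit 11: 54–60 (7 days) |
| Window with 5 days early | 24–32 (9 days) | 52–60 (9 days) |

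The overlap is 7/15 = 47% of allowed EOT days, or 9/15 = 60% with the exceptional allowance. These are counts of days, not probabilities. ET has no window, so its share cannot be computed. An EOT score can therefore be recovered by 4.4 at week 4 or 8 and then removed by 6.3.7.2 or 6.3.8.

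**4. How many patients could be involved?**

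- Inputs from SAP 2.5: about 440 completing week 8, about 640 randomized, ratio 1:1:1:1.
- Planned non-completion: 1 − 440/640 = 31.25%, that is 640 − 440 = 200 patients.
- Per arm: 640/4 = 160 randomized, 440/4 = 110 completing, so 50 not completing.
- The share of these with a usable score after withdrawal is not given. Assuming 10%, 25% or 50%, scores would be lost for 200 × 0.10 = 20, 200 × 0.25 = 50 or 200 × 0.50 = 100 patients.

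**5. By-visit PSP under its own estimand.** SAP 6.3.2.2 follows the steps of 6.2.4, whose model has a treatment-by-visit term. It can therefore give week 4 as well as week 8 from the imputed data. Section 6.3.8 does not refer to it.

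**The case against.** The strongest reply is that these sentences are residue. The SAP amendment history records deletion of the while-on-treatment strategy, and 1.2.3, 1.2.4, 6.3 and 17.3 agree on what is intended, so this is editing in lower-tier endpoints. That is a plausible origin, but the sentences are operative instructions in the sections a programmer would follow.

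Other points:

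- **Missing text.** A figure is not shown just before the SQLS restriction, and the other-secondary rows of Appendix D are redacted. Neither is relied on here, and neither can cancel the explicit wording of 1.2.3 and 6.3.
- **PSP differs from SQLS.** This stands. Section 6.3.8 names no estimand, so its conflict is with 1.2.3, 1.2.4 and 6.3 rather than internal. Read as a separate on-treatment analysis, it would leave treatment-policy PSP at week 4 with no dedicated method text.
- **The removal rule fits the primary-estimand half of 6.3.7.2.** Partly so. But Table 1 of the SAP already governs removal there, and 6.3 does not allow that analysis for SQLS.
- **Depot coverage.** The SAP does not say whether the 4 weeks after an injection count as receiving randomized treatment. If they do, fewer scores are lost. The rule still deletes anything after withdrawal, so the texts still conflict.
- **Size.** The 31% is back-calculated from planning numbers because the early-termination rate is redacted, and the protocol amendment reports 675 randomized by 29 January 2024. It is a planning bound, not an observed one.
- **Imputation.** An MMRM can handle the missing-at-random events without imputation. The reference-based events of the primary estimand cannot be handled that way.

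**Conclusion.** The concern holds. For SQLS the contradiction lies within one section. For PSP it lies between 6.3.8 and the estimand sections. Followed as written, the SAP reports on-treatment estimates where it promises treatment-policy and modified treatment-policy ones.

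The effect is confined to SQLS and the 6.3.8 PSP analysis. The primary PANSS analysis and the key secondary week-8 PSP analysis under 6.3.2.2 do not change. The number of scores lost is probably small and depends on two things the documents do not give: how many patients who stopped have an in-window ET or EOT score, and whether depot coverage counts as treatment. The contradiction itself depends on neither. It should be corrected, with high confidence that the texts conflict.

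**What to change.** Before the first database lock:

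1. In 6.3.7.2 and 6.3.8, delete the sentence limiting the analysis to on-treatment scores and the one setting later values to missing. Alternatively, move them to a supplementary on-treatment analysis that is labelled as such and listed in 1.2, 6.3 and Appendix D.
2. Limit the bar on multiple imputation to the treatment-policy and modified treatment-policy analyses. Protocol 10.5.6.3 assumes missing at random for the primary and key secondary endpoints under treatment policy. State that the same assumption is extended to SQLS and week-4 PSP.
3. Reconcile 6.3.7.2 with 6.3 on the primary-estimand SQLS analysis. Either delete that clause, or amend 6.3, permit imputation and let Table 1 of the SAP govern which scores are removed.
4. In 6.3.8, state that by-visit PSP under the key secondary estimand at weeks 4 and 8 comes from the imputed-data model of 6.2.3–6.2.4 as used in 6.3.2.2.

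The cost is a few sentences in two sections (plus 6.3 if the primary-estimand SQLS analysis is kept) and one derivation flag, with no new data. Keeping an on-treatment analysis as supplementary adds one output per endpoint and the listing entries in item 1.

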6.4. Other Efficacy Endpoints Analysis

6.4.1. Positive and Negative Symptom Scale (PANSS) – Change From Baseline to End of Treatment Period in Period 2

6.4.1.1. Definition

See Section [6.2.1](#).

6.4.1.2. Analysis

MMRM model will be repeated for this endpoint

```
proc mixed data=data method=reml;
  class trt01pn avisitn subjid;
  model variable = trt01pn avisitn trt01pn*avisitn sex region age
baseline/ddfm=kr cl;
  repeated avisitn/subject=subjid type=un;
  lsmeans trt01pn*avisitn/cl;
run;
```

Results Presentation

Summary statistics will be produced for absolute and change from period 2 baseline, by timepoint and treatment (TV-44749 318mg, TV-44749 425mg, TV-44749 531mg and former placebo assignment, i.e., overall 6 groups for period 2)

Least-square means of absolute value and change from baseline, including standard errors and 95% CI, will be presented at each timepoint by treatment group.

6.4.2. Clinical Global Impression-Severity (CGI-S) – Change From Baseline to End of Treatment Period in Period 2

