2.2. Randomization and Blinding

Period 1: Patients will be randomized to receive 1 of 3 doses of TV-44749 (low [318 mg q1m], medium [425 mg q1m], or high dose [531 mg q1m]) sc injection or placebo sc injection in a 1:1:1:1 ratio. Randomization will be stratified by sex (male or female) and geographical region (North America; Europe and Asia, namely, the continent of Europe and India; Far East, namely China; and the rest of the world). The doses of TV-44749 will be comparable to low, medium, and high dose of oral olanzapine (10, 15, and 20 mg, respectively). Patients randomized to TV-44749 or placebo sc will receive a sc injection of TV-44749 or placebo, respectively, at baseline (randomization) and visit 7 (week 4).

During Period 1, patients and investigators will remain blinded to the identity of the treatment administered to each patient. Due to the differences between TV-44749 and placebo, unblinded study personnel, not associated with rating the patient and assessments of safety and independent of the study team, will be required at each site to reconstitute and administer the IMP. The sponsor's clinical personnel (and delegates) involved in the study will be blinded to the identity of the IMPs until the Period 1 database is locked for final efficacy analysis. The sponsor (and/or delegates) will assign designated unblinded personnel who will be responsible to oversee unblinded activities performed at the site during Period 1. This includes but is not limited to unblinded monitoring at the site and supporting the unblinded site staff as required during Period 1. During Period 1, the sponsor's (and delegates) unblinded personnel will not be involved with managing the study and will not take part in any discussions or decisions related to it.

Period 2: Period 2 will be open-label and will not include a placebo group. Period 1 will remain blinded until database lock for Period 1. In order to maintain the blind in Period 1, all patients will be randomized again between Period 1 and Period 2.

Patients will be randomized to receive 1 of 3 doses of TV 44749 sc injection (low [318 mg q1m], medium [425 mg q1m], or high dose [531 mg q1m]). After completing all visit 11 (week 8) scales and assessments, eligible patients who were on active treatment in Period 1 will retain their Period 1 treatment assignment, and eligible patients who were on placebo in Period 1 will be randomized to one of the active treatment groups in 1:1:1 ratio. To maintain the blind in

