3. ANALYSIS SETS

3.1. Full Analysis Set

The full analysis set will include all patients randomized to Period 1 regardless of the actual treatment the patients received.

The treatment assignment for this analysis set will be according to the randomization assignment in the opening of each Period (Visit 2 for Period 1 and Visit 11 for Period 2).

This analysis set will be used for selected exploratory efficacy analyses and supplementary analyses, unless otherwise specified.

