6.2.4. Primary Analysis

For each of the 200 complete datasets, a mixed model repeated measures (MMRM) analysis will be performed using the change in PANSS score from baseline to week 8 as the dependent variable, and treatment arm, study visit, treatment-by-visit interaction, stratification variables (sex and geographic region), age, and PANSS total score at baseline as covariates. An unstructured covariance matrix will be used in all models. Analyses will be performed in SAS using the Kenward-Roger option to estimate the denominator degrees of freedom and standard errors. If the group size of stratification factors is small, groups may be pooled together for modeling purposes. Such a decision will be made prior to unblinding and documented in the statistical data review meeting.

Least squares means will be calculated of the change from baseline to week 8 in the PANSS total score for each of the 4 treatment arms and for the differences between each of the TV-44749 arms and the placebo arm. In addition, the 95% confidence intervals, and the nominal p-values

for the comparisons between each of the 3 dose strengths of TV-44749 and placebo will be calculated using PROC MIANALYZE using Rubin's rules (see [Appendix B](#) for further details and example code). The nominal p-values will be adjusted for multiplicity (see Section [7](#)).

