APPENDIX B. MULTIPLE IMPUTATION DETAILS**Primary Analysis****Data preparation**

Intercurrent events (ICEs) are defined in [Table 1](#) (Section 1.2.1). Visits where an ICE occurred will be labelled with the appropriate ICE type:

USUBJID	TRT01P	AVISITN	AVISIT	ADY	AVAL	CNSRDT	EVNTDESC
██████████	Placebo	4		Visit 4/ Week 1		██████████	
██████████	Placebo	5	██████████	Visit 5/ Week 2	2	██████████	Prohibited antipsychotic
██████████	Placebo	6		Visit 6/ Week 3	2	██████████	Prohibited antipsychotic
██████████	Placebo	7		Visit 7/ Week 4	2	██████████	Prohibited antipsychotic
██████████	Placebo	8		Visit 8/ Week 5	2	██████████	Prohibited antipsychotic
██████████	Placebo	9		Visit 9/ Week 6	2	██████████	Prohibited antipsychotic
██████████	Placebo	10		Visit 10/ Week 7	2	██████████	Prohibited antipsychotic
██████████	Placebo	11		Visit 11/ Week 8	2	██████████	Prohibited antipsychotic

The classification of intercurrent events (ICEs) will be performed as follows:

Event	CNSR	EVNTDESC
Early termination from randomized treatment due to "Lack of Efficacy" or an Adverse Event of "Exacerbation of schizophrenia"	1	ET due to lack of efficacy
An oral antipsychotic use was documented in the CRF (Concomitant Medication or Protocol Deviations) and reviewed in a blinded manner in the statistical data review meeting and does not meet the conditions in Section 1.2.1	2	Prohibited antipsychotic
Early termination from randomized treatment due to other reasons	3	ET due to other reasons

Multiple Imputation Method

[figure not shown]
Parameter Estimation Model

Imputation of ICE data under MAR

Imputation of ICE data under MNAR

[figure not shown]

Analysis model

[figure not shown]
Tipping Point Analysis (Two dimensional)

Tipping Point Analysis (One dimensional)

[figure not shown]
[figure not shown]
[figure not shown]
[figure not shown]
[figure not shown]
The above process will be repeated, but the delta value for the placebo group will be held at zero. The range of delta values and increments may be adjusted post hoc depending on the observed treatment effect in order to most effectively characterize the “tipping point”.

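### The printed Period 2 MMRM leaves sex and region out of CLASS, and its one treatment variable, not defined in the visible SAP, gives 4 or 3 LS-mean groups under the documented assignments, against the 6 groups named beside it

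*SAP*

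**What the plan says.** The code in SAP 6.4.1.2 declares three categorical variables: "class trt01pn avisitn subjid". The model line contains treatment (`trt01pn`), visit, their interaction, sex, region, age and baseline. LS means are requested for treatment by visit, with confidence limits and no differences. Sections 6.4.2.2 (CGI-S), 6.4.3.2 (PSP) and 6.4.6.2 (SQLS) refer back to this model.

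Below the code, one results heading covers two sentences. The first asks for summary statistics by the three doses and "former placebo assignment, i.e., overall 6 groups for period 2", with change measured from the Period 2 baseline. The second reads: "Least-square means of absolute value and change from baseline, including standard errors and 95% CI, will be presented at each timepoint by treatment group". It names neither the groups nor which baseline.

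Four other places bear on the point:

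- SAP 3.1 assigns treatment in the full analysis set "according to the randomization assignment in the opening of each Period (Visit 2 for Period 1 and Visit 11 for Period 2").
- SAP 2.2 says that eligible former-placebo patients are "randomized to one of the active treatment groups in 1:1:1 ratio", and that Period 1 randomization is "stratified by sex (male or female) and geographical region (North America; Europe and Asia", with Far East and rest of the world as the other two regions.
- SAP 6.2.4 lists "stratification variables (sex and geographic region), age, and PANSS total score at baseline as covariates" and allows small strata to be pooled.
- SAP Appendix B shows an example data table headed "USUBJID TRT01P AVISITN AVISIT", in which the treatment column holds the placebo arm through Visit 11.

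**The concern.** There are two separate problems in one block of code.

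The first is the CLASS statement. In PROC MIXED, a variable that is in MODEL but not in CLASS is treated as a continuous covariate. For nominal regions that is not the model that SAP 6.2.4 describes.

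The second is the treatment variable. The design produces six treatment paths in Period 2, and the summary-statistics sentence recognises them. The model has a single treatment term, the visible SAP does not say what it contains, and neither assignment that the SAP documents has six levels. Two programmers, one following SAP 3.1 and one following the Appendix B table, would produce different LS-mean tables from the same plan. Neither table would line up with the six-group descriptive table beside it.

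At stake are the readability and reproducibility of the model-based Period 2 estimates for four scales.

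**Working it through.** **Reproducing the figure of six.** SAP 2.1 gives four Period 1 arms: 318, 425 and 531 mg, and placebo. Active patients keep their dose at Visit 11 (3 paths). Placebo patients are split over the three doses (3 paths). 3 + 3 = 6, which agrees with the SAP.

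**Levels of each documented coding of `trt01pn`.**

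| Coding | Source | Levels | What is combined in the LS means |
|---|---|---|---|
| Period 1 arm | variable name; Appendix B table | 4 | former-placebo patients on 318, 425 and 531 mg form one group |
| Visit 11 assignment | SAP 3.1 | 3 | former-placebo patients join those continuing the same dose |
| Period 1 arm by initial Period 2 dose | not stated | 6 | nothing |

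**LS means per response.** The count is groups times post-baseline time points. Time points come from Protocol Table 2 and Appendix B.

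- PANSS and CGI-S: visits 12 to 22 are 11 visits, plus end of treatment, so 12. Each scale has 4 × 12 = 48 or 3 × 12 = 36 LS means, against 6 × 12 = 72.
- PSP and each SQLS score: visits 14, 17 and 20 plus end of treatment, so 4. Each has 4 × 4 = 16 or 3 × 4 = 12, against 6 × 4 = 24.

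The SAP asks for both absolute value and change, and SQLS has a total and two subscale scores. The overall totals are therefore larger, in the same ratios of 4:6 and 3:6.

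**Effect of the CLASS omission.** At one visit, the number of fixed-effect parameters is

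1 (intercept) + (groups − 1) + 1 (sex) + region df + 1 (age) + 1 (baseline),

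with region df = 1 if numeric and 4 − 1 = 3 if categorical and unpooled.

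| Groups | Region numeric | Region in CLASS |
|---|---|---|
| 4 | 1 + 3 + 1 + 1 + 1 + 1 = 8 | 10 |
| 3 | 1 + 2 + 1 + 1 + 1 + 1 = 7 | 9 |
| 6 | 1 + 5 + 1 + 1 + 1 + 1 = 10 | 12 |

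Fits to simulated data gave the same ranks. The gain of 2 comes entirely from region. Sex has two levels and takes 1 df either way. A numeric sex gives the same fitted values and the same treatment differences, but its LS means are evaluated at the mean of the sex variable instead of at equal weights. If regions are pooled to two levels, region behaves in the same way. If either variable is stored as character, the procedure stops with an error.

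**The case against.** The strongest reply is that this is template code. The data set, response and baseline names are placeholders, so `trt01pn` may be one too. Both presentation sentences sit under one heading, and the natural reading is that the LS means use the six groups just named. SAP 6.2.4 leaves no doubt that sex and region are categorical, so a programmer would correct the CLASS line, and a character variable would force the correction.

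Much of this stands. Intended six-group LS means are a reasonable inference, and a six-level variable stored under this name would remove the mismatch. But the SAP does not say so, and the two assignments that it does document point elsewhere. A numeric region would run without any error to prompt a correction.

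Three further limits apply. The model code in Appendix B is not shown, so the lack of a definition can be claimed only for the visible text. The Appendix B table is a Period 1 example and weak evidence for Period 2 coding. The storage type of region is not given, so that harm is conditional.

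A reader might also infer that the SAP contradicts itself on the number of LS-mean groups. It does not go that far: the count of six belongs to the summary statistics, and the LS-mean sentence gives no number. Nor would former-placebo patients vanish from Period 2 reporting, because the six-group descriptive statistics keep them separate under either coding.

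**Conclusion.** The point holds as a minor error in stated code. The CLASS omission is plain on the page. Its consequence depends on coding: a stop if character, or 1 df instead of up to 3 if region is numeric and keeps three or more levels. The treatment term gives 4 or 3 LS-mean groups per visit under the documented assignments, against six in the adjacent descriptive table. Which one applies cannot be settled from the visible text.

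The reach is narrow. Only the open-label Period 2 analyses grouped as other efficacy endpoints are affected. The code requests no between-group contrast, and SAP 6.1 confines primary and secondary efficacy to Period 1 data. A reader might infer that the primary or key secondary results are at risk; nothing here supports that. Dose changes allowed from visit 12 (SAP 2.1) also limit what any grouping by initial assignment can show.

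**What to change.** - Add sex and region to the CLASS statement in SAP 6.4.1.2.
- Replace `trt01pn` with a defined six-level variable, Period 1 arm by initial Period 2 dose, in CLASS, MODEL, the visit interaction and LSMEANS. Period 2 dose, a former-placebo indicator and their interaction would give the same fit.
- State that the LS means are presented for the same six groups as the summary statistics.
- Label the baseline covariate and the LS-mean change as referring to the Period 2 baseline of SAP 4.2.

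The references from CGI-S, PSP and SQLS then carry the correction. The cost is a few words of code and text, with no new data. The SAP amendment is dated 17 April 2024 and the last patient's last visit was planned for Q2 2025, so the wording could be settled before the final Period 2 tables are programmed.
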